## 6.4.2 Primary Efficacy Analysis

The primary efficacy endpoint is the change from baseline in mean monthly MPM headache days across the 12-week treatment period. The endpoint will be analyzed using MMRM. The response variable is the change from baseline to each postbaseline month in monthly MPM headache days. The model will include baseline monthly MPM headache days as a covariate, treatment group and visit (month) as fixed factors, and treatment group-by-visit and baselineby-visit as interaction terms. The analysis will be performed based on evaluable postbaseline data using only the observed cases without imputation of missing values.

Restricted maximum likelihood method will be used. The within-patient correlation will be modeled using the unstructured covariance matrix. If the model does not converge, then the compound symmetry covariance structure will be used. The Kenward-Roger approximation will be used to estimate denominator degrees of freedom. Contrasts will be constructed to obtain the average treatment effects across the 12-week treatment period to compare each atogepant treatment group versus the placebo group. Each treatment effect and treatment comparisons will be estimated by the LS Means and their differences in LS Means, along with their SE and 95% confidence intervals, and the p-value corresponding to the betweentreatment group difference.

#### 6.4.3 Sensitivity Analysis

#### 6.4.3.1 Pattern-Mixture Model

The sensitivity analysis will use a pattern-mixture model (PMM) approach based on the *reference-based* copy reference method (Carpenter et al, 2013) for missing value imputation. *This approach considers a missing-not-at-random (MNAR) mechanism for missing data and is to assess the impact of potential deviation of MAR assumption in the primary analysis.* 

Note that the missingness is assumed monotonic. Any intermediate missing values, if any, will be imputed at first. If the intermediate missing value exists at the first postbaseline month, it is imputed using the average of baseline and next available postbaseline values; otherwise, intermediate missing values are imputed using last observation carried forward (LOCF) approach.

The details of missing data imputation using the copy reference method are as follows:

- 1. The reference-based approach uses the placebo group as the reference. The missing values in the reference group are imputed using the observed data in that group under the missing-at-random assumption. The missing pattern is defined by the participant's last visit with a non-missing value. The mean vector and the covariance matrix of the multivariate normal distribution are estimated for reference group.
- 2. For atogepant treatment groups, missing values are imputed based on the distribution estimated from the reference group (from Step 1).
- 3. The MI (Step 1 and 2) will be performed 20 times and result in 20 imputed datasets. Each of the 20 imputed datasets will be analyzed using ANCOVA model. For a given imputed dataset, the average change from baseline in monthly MPM headache days is calculated across the 3 post-baseline months and is used as the response variable in the model. The model includes treatment group as a fixed factor and baseline monthly MPM headache days as a covariate. The LS mean difference and corresponding SE is estimated from the model comparing each atogepant treatment group with the placebo group.
- 4. The ANCOVA analysis results from 20 completed datasets are combined for overall estimation and inference using Rubin's rule (1987) to produce a pooled estimate of LS mean difference, its SE, and corresponding p-value for the test of null hypothesis of no treatment effect.

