5.1.1.1 Common Conventions

5.1.1.1.1 Analysis Populations

The analysis populations will consist of participants as defined below:

Population Definition		Study Treatment
Screened	All screened participants who sign informed consent	—
Intent-to-Treat (ITT)	All randomized participants	Randomized assignment
Modified Intent-to- Treat (mITT)	 All randomized participants who received ≥ 1 dose of study treatment, had an evaluable baseline period of diary data, and had ≥ 1 evaluable post-baseline 4-week (Weeks 1-4, 5-8, and 9-12) of diary data For baseline, evaluable is defined as having at least 20 days of diary data during the 4-week baseline period For each post-baseline 4-week treatment period, evaluable is defined as having at least 12 days of diary data for that particular period 	Randomized assignment
Safety	ty All participants who received ≥ 1 dose of study treatment Actual received	

Table 5–1Analysis Populations

¹ Participants will be summarized according to the study treatment received for majority of treatment period.

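### The copy-reference sensitivity analysis first fills intermittent missing months with a single fixed value, so it departs from the MMRM by more than the copy-reference assumption; the effect is small

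*SAP*

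**What the plan says.** SAP 6.4.3.1 sets out the pattern-mixture sensitivity analysis of the primary endpoint. It assumes monotone missingness and removes whatever breaks that assumption at the start: "Any intermediate missing values, if any, will be imputed at first". The rule for a Month 1 gap reads: "it is imputed using the average of baseline and next available postbaseline values". A second clause, which with three months can reach only Month 2, covers the rest: "otherwise, intermediate missing values are imputed using last observation carried forward (LOCF) approach".

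The copy-reference steps follow, and only they are repeated: "The MI (Step 1 and 2) will be performed 20 times and result in 20 imputed datasets". Step 1 states: "The missing pattern is defined by the participant's last visit with a non-missing value". On the placebo arm it adds: "The missing values in the reference group are imputed using the observed data in that group under the missing-at-random assumption". Step 3 averages the three months in each dataset and fits an ANCOVA. Step 4 pools by Rubin's rule.

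The primary MMRM (SAP 6.4.2) is fitted "using only the observed cases without imputation of missing values", with MAR assumed (SAP 5.1.1.1.4). A post-baseline month counts as missing when the diary is too thin; SAP 5.1.1.1.1 says "evaluable is defined as having at least 12 days of diary data for that particular period".

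Protocol 7.3.1 asks for reference-based multiple imputation and mentions neither LOCF nor averaging with baseline.

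**The concern.** The SAP gives the purpose of this analysis as testing how far the primary result depends on MAR. For that, it should differ from the MMRM mainly in what it assumes about missing data after dropout. It also changes the handling of gaps in patients who come back, using a deterministic rule for which no reason is given.

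Three things follow.

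- The filled values are the same in all 20 datasets, so Rubin's rule treats them as known.
- The Month 1 rule has a built-in direction: it moves an improving patient towards no change. Its effect on the treatment difference depends on which arm has more Month 1 gaps.
- A difference between this analysis and the MMRM cannot be put down to the copy-reference assumption alone.

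**Working it through.** **Order of steps.** The fill has no random part and comes before Steps 1 and 2. Only those two steps are performed 20 times, so the fills are constant across datasets. The missingness pattern is set by the last non-missing month, so a filled gap no longer counts as missing. Nothing keeps filled placebo values out of the reference mean and covariance. The SAP does not say in words that fills are treated as observed; that follows from this sequence.

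**Inputs from the documents.** Effect −1.5 days for 60 mg QD, SD 3.0, 180 per arm (protocol 7.7; SAP 5.1.2); 20 imputations, ANCOVA and Rubin's rule (SAP 6.4.3.1). The plan gives no figure for intermittent gaps. As a check on the inputs, the complete-data SE is 3.0 × √(2/180) = 0.316. Power at two-sided alpha 0.025 is Φ(1.5/0.316 − 2.241) = 99.4%, against the stated 99.3%.

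**Assumptions not in the documents.** Gap rates, monthly profiles, between-month correlation 0.6 and 12% monotone dropout.

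**Shift per affected Month 1 patient.** The filled change is half the next observed month's change. The shift on the three-month mean is therefore (½ × next change − true Month 1 change)/3.

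- Rising profile, placebo −2.0/−2.6/−2.9: (−1.3 + 2.0)/3 = 0.23 day.
- The same with a constant −1.5 effect, active −3.5/−4.1/−4.4: (−2.05 + 3.5)/3 = 0.48 day.
- Flat profile, used in the main simulation below: placebo 2.5/6 = 0.42 day, active 4.0/6 = 0.67 day.

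**Shift in the treatment difference, equal gap rates.** The main simulation (flat profile, 60 mg QD versus placebo, gaps split evenly between Months 1 and 2, 250 runs) applied the SAP fill and MCMC imputation of the gaps to the same datasets. Entries are the mean estimate (mean SE).

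| Gap rate, each arm | SAP fill | MI of gaps | Difference |
|---|---|---|---|
| 2% | −1.491 (0.320) | −1.493 (0.321) | 0.002 |
| 5% | −1.462 (0.320) | −1.470 (0.321) | 0.008 |
| 10% | −1.462 (0.320) | −1.472 (0.322) | 0.010 |

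A separate simulation (200,000 per arm, rising profile, fill compared with complete data) gave shifts of 0.001, about 0.005 and about 0.007 day at 1%, 3% and 5%.

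**Unequal Month 1 gap rates (400 runs).** Expected shift = active rate × active shift − placebo rate × placebo shift. A negative value favours the active arm.

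| Placebo / active gaps | Expected shift | SAP fill | MI of gaps | Difference |
|---|---|---|---|---|
| 10% / 2% | 0.02 × 0.667 − 0.10 × 0.417 = −0.028 | −1.502 | −1.475 | −0.027 |
| 2% / 10% | 0.10 × 0.667 − 0.02 × 0.417 = +0.058 | −1.371 | −1.429 | +0.058 |
| 10% / 0%, no true effect | 0 − 0.10 × 0.417 = −0.042 | −0.032 | +0.009 | −0.041 |

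**Variance and type I error.** The SE is about 0.001–0.003 smaller with the fill, that is, under 1%. With no true effect and 10% gaps in both arms, rejection at two-sided 5% was 0.045 with the fill and 0.048 with MI of the gaps. With 400 runs the Monte Carlo error is about √(0.05 × 0.95/400) = 0.011, so this rules out only gross inflation.

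**Months 1 and 2 missing, Month 3 observed.** One evaluable period is enough for the mITT population, so such a patient is analysed. Let the Month 3 change be d. Month 1 is filled as d/2. Month 2 falls under LOCF, but there is no observed post-baseline value to carry.

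- Carrying the filled Month 1 gives (d/2 + d/2 + d)/3 = 2d/3.
- Carrying baseline gives (d/2 + 0 + d)/3 = d/2.

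Two programmers could follow the same text and differ by d/6 for that patient.

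**The case against.** The rule is prespecified, belongs to a supportive analysis and does not contradict the protocol. Its reach is narrow. A Month 3 gap is always monotone, so LOCF can only touch Month 2. A month is lost only with fewer than 12 diary days, and a missed entry can be completed the next day. At equal gap rates with a true effect, the fill moved the estimate towards zero in every setting, which is the cautious direction. Strict attribution was never available in any case, because Step 3 also replaces the MMRM by an ANCOVA on the three-month mean. All of this stands, and it is why the point is minor. It does not give a reason for the fill, make it conservative when placebo has more Month 1 gaps, or settle the case where only Month 3 is observed.

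A reader might infer more than the documents support:

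- **That standard errors are materially understated or type I error is inflated.** The calculations show neither.
- **That an affected patient's change is halved.** The rule halves the next month's change and uses it for Month 1 only. Under the rising profile the three-month mean loses 0.23 of 2.5 days on placebo (about 9%) and 0.48 of 4.0 on active (about 12%).
- **That the analysis was promised as an isolated test of missing-not-at-random data after dropout.** The SAP states the broader aim of robustness to departures from MAR.

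**Conclusion.** The point holds as a minor weakness in one sensitivity analysis. Intermittent gaps receive a single unexplained value, fixed across all 20 datasets, and the rule is incomplete for one missing-data pattern. The primary MMRM is not affected.

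In size, the treatment difference moves by about 0.001–0.01 day at equal gap rates of 1–10%, and by up to about 0.06 day when Month 1 rates are 2% and 10%. The largest shift, 0.058 day, is about 0.18 of one SE (0.058/0.320), against assumed effects of 1.2–1.6 days. An affected Month 1 patient moves by about 0.2–0.5 day on the three-month mean under the rising profile, and by more (0.42–0.67 day) under the flat one. These sizes rest on assumed gap rates, profiles, correlation and dropout. The direction depends on the balance of Month 1 gaps between arms, which the documents do not give.

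**What to change.** Replace the fill in SAP 6.4.3.1. Within each of the 20 imputations, impute intermittent gaps by MCMC under MAR within treatment arm, then apply copy reference to the remaining monotone tail. Keep the ANCOVA and Rubin's rule as planned. This also settles the case of Months 1 and 2 missing with Month 3 observed. Report the number of intermittent gaps by arm, separately for Months 1 and 2.

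The cost is one extra imputation step and a few lines of text. SAP 6.4.3.2 already uses MCMC imputation, and protocol 7.3.1 needs no amendment because it specifies only reference-based multiple imputation. SAP 5.1 places approval of the SAP before database lock, so the change can be prespecified if it is made by then.

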#### 6.4.3.2 Robust Regression

The sensitivity analysis uses MI in conjunction with robust regression to assess the robustness of the primary MMRM analysis to the possible violation of normality assumption. This method has been described and referred as ADAP [R] in Mehrotra et al. 2012. The details of method are as follows.

The normality test is performed on the residuals which are generated by the same MMRM as used for the primary efficacy analysis. The residuals are scaled by the inverse Cholesky root of its estimated variance-covariance matrix. The Kolmogorov-Smirnov (K-S) test for normality is applied to the de-correlated and scaled residuals and normality test is rejected if p-value from the K-S test is less than 0.01.

If the normality test is rejected, sensitivity analysis below will be performed:

- 1. Create complete datasets using MI based on the Markov chain Monte Carlo (MCMC) approach. Imputed data will consist of 20 complete datasets.
- 2. Each of the 20 complete datasets will be analyzed using robust regression (Mestimation) to protect against either observed outliers in the original incomplete dataset, or imputed outliers in the completed datasets. For a given complete dataset, the average change from baseline in monthly MPM headache days is calculated across the 3 postbaseline months and is used as the response variable in the robust regression model. The model includes treatment group as a fixed factor and baseline monthly MPM headache days as a covariate. The mean difference and corresponding SE is estimated from the model comparing each atogepant treatment group with the placebo group.
- 3. The robust analysis results from 20 completed datasets are combined for overall estimation and inference using Rubin's rule (1987) to produce a pooled estimate of treatment difference, its SE, and corresponding p-value for the test of null hypothesis of no treatment effect.

#### 6.5 Safety Endpoint Conventions

#### 6.5.1 Adverse Events

#### 6.5.1.1 Missing Intensity or Relationship

If the investigator is unable to provide the actual values, the following imputations will be applied:

Missing Value	Imputation	Timing
Intensity	Mild	Screening Period
	Severe	Treatment Period
Relationship		Screening Period
	Related	Treatment Period

 Table 6–6
 Missing AE Intensity and Relationship Imputation Algorithms

#### 6.5.2 Clinical Laboratory Assessments

#### 6.5.2.1 Potentially Clinically Significant Criteria

Laboratory assessments values meeting any of the following PCS low or PCS high criteria will be categorized as PCS:

#### Table 6–7 Clinical Laboratory PCS Criteria

			PCS Criteria	
Category	Parameter	SI Unit	PCS Low	PCS High

			PCS C	Criteria
Category	Parameter	SI Unit	PCS Low	PCS High
Chemistry	Albumin	g/L	$< 0.8 \times LLN$	$> 1.2 \times ULN$
-	Alanine aminotransferase	U/L		$\geq$ 3.0 × ULN
	Alkaline phosphatase	U/L		$\geq$ 3.0 × ULN
	Aspartate aminotransferase	U/L		$\geq$ 3.0 × ULN
	Bicarbonate	mmol/L	$< 0.9 \times LLN$	$> 1.1 \times ULN$
	Bilirubin, total	µmol/L		$\geq$ 1.5 × ULN
	Blood urea nitrogen	mmol/L		$> 1.5 \times ULN$
	Calcium	mmol/L	$< 0.9 \times LLN$	$> 1.1 \times ULN$
	Chloride	mmol/L	$< 0.9 \times LLN$	$> 1.1 \times ULN$
	Cholesterol, total	mmol/L		$> 1.6 \times ULN$
	Creatinine	µmol/L		$> 1.5 \times ULN$
	Creatine kinase	U/L		$> 2.0 \times ULN$
	Estimated glomerular filtration rate	mL/min/1.73m ²	$< 0.8 \times LLN$	
	Glucose, nonfasting	mmol/L	$< 0.8 \times LLN$	$> 2.0 \times ULN$
	Lactate dehydrogenase (LDH)	U/L		$> 3.0 \times ULN$
	Phosphorus	mmol/L	$< 0.9 \times LLN$	$> 1.1 \times ULN$
	Potassium	mmol/L	$< 0.9 \times LLN$	$> 1.1 \times ULN$
	Protein, total	g/L	$< 0.9 \times LLN$	$> 1.1 \times ULN$
	Sodium	mmol/L	$< 0.9 \times LLN$	$> 1.1 \times ULN$
	Triglycerides	mmol/L		$> 2.0 \times ULN$
	Uric acid	µmol/L		$> 1.2 \times ULN$
Hematology	Basophils, absolute cell count	10 ⁹ /L		$> 2.0 \times ULN$
	Eosinophils, absolute cell count	10 ⁹ /L		$> 2.0 \times ULN$
	Hematocrit	Ratio	$< 0.9 \times LLN$	$> 1.1 \times ULN$
	Hemoglobin	g/L	$< 0.9 \times LLN$	$> 1.1 \times ULN$
	Lymphocytes, absolute cell count	10 ⁹ /L	$< 0.7 \times LLN$	$> 1.3 \times ULN$
	Monocytes, absolute cell count	10 ⁹ /L	$< 0.5 \times LLN$	$> 2.0 \times ULN$
	Neutrophils, absolute cell count	10 ⁹ /L	$< 0.7 \times LLN$	$> 1.3 \times ULN$
	Platelet count	10 ⁹ /L	$< 0.5 \times LLN$	$> 1.5 \times ULN$
	Red blood cell count	10 ¹² /L	$< 0.9 \times LLN$	$> 1.1 \times ULN$
	White blood cell count	10 ⁹ /L	$< 0.9 \times LLN$	$> 1.5 \times ULN$
Urinalysis	pH	pH	$< 0.9 \times LLN$	$> 1.1 \times ULN$
	Glucose	mmol/L		Positive ¹
	Protein	g/L		Positive ²
	Specific gravity	_		$> 1.1 \times ULN$

LLN = lower limit of normal value; ULN = upper limit of normal value; normal value provided by laboratory. SI = Le Système International d'Unités (International System of Units). ¹ Any results other than negative will be considered as positive. ² Any results other than trace or negative will be considered as positive.

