6.4.3 Clinical Laboratory Determinations

Blood and urine samples for clinical laboratory tests will be collected at the visits outlined in Table 1-1. Hematology, chemistry, and urinalysis will be conducted at these visits. Serology, coagulation parameters (INR), and the Urine drug screen will be conducted at Screening (Visit 1). The investigator will assess the clinical significance of any values outside the reference ranges provided by the central laboratory. Patients with abnormalities judged to be clinically significant at Screening (Visit 1) or with positive results on the urine drug screen will be excluded from the study.

Women of childbearing potential will be required to have a urine pregnancy test at all visits. A positive pregnancy test at Visit 1 or Visit 2 will exclude the patient from participation in the study.

Investigators may also perform unscheduled clinical laboratory determinations at any time for the purpose of patient safety.

Patients are not required to fast overnight before coming in for their appointments.

The clinical laboratory parameters to be measured are shown in [Table 6–1](#).

Table 6–1 Clinical Laboratory Parameters

Category	Parameter
Chemistry	Sodium, potassium, chloride, bicarbonate, glucose, blood urea nitrogen, creatinine, total bilirubin, alkaline phosphatase, aspartate aminotransferase, alanine aminotransferase, lactate dehydrogenase, creatine kinase, total protein, albumin, calcium, phosphorus, uric acid, total cholesterol. The estimated glomerular filtration rate will be calculated by the central laboratory.
Hematology	Hemoglobin; hematocrit; red blood cell count; red blood cell indices (mean corpuscular volume, mean corpuscular hemoglobin, mean corpuscular hemoglobin concentration); white blood cell count, including differential (neutrophils, lymphocytes, monocytes, eosinophils, and basophils); platelet count
Urinalysis	Urine dipstick for specific gravity, pH, protein, glucose, ketones, bilirubin, and blood; microscopic exam including red blood cells/high-power field, white blood cells/high-power field, and casts/low-power field.
Coagulation	At Visit 1 only: international normalized ratio
Serology	At Visit 1 only: anti-hepatitis A IgM antibody, hepatitis B surface antigen, anti-hepatitis C antibody

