## 6.2.2 Safety

The analysis visit windows for safety endpoints are defined as follows:

Analysis Phase	Analysis Visit (Derived)	Scheduled Study Visit (eCRF)	Window
Pretreatment	Baseline	Visit 2	Treatment Day $\leq 1$
		(Randomization)	
Treatment	Week 2	Visit 3	Treatment Day [2, 20]
	Week 4	Visit 4	Treatment Day [21,34]
	Week 6	Visit 5	Treatment Day [35, 48]
	Week 8	Visit 6	Treatment Day [49, 69]
	Week 12	Visit 7/ET	Treatment Day [70, the last double-blind visit]
	End of treatment		Last available assessment during double blind
			treatment period
	Week 16 (Safety	Visit 8	Treatment Day [the last double-blind visit +1, the
	follow-up)		last study visit]
	End of study		Last available assessment after treatment start date,
			i.e. occurs at final visit (expected Day 112) or ET

Table 6–3Safety Analysis Visit Definitions

Safety follow-up visit will be presented in analysis tables for clinical laboratory values and vital signs. End of Treatment is defined as the last available assessment during double-blind treatment period, i.e. on or before the treatment end date. End of Treatment results will be presented in analysis tables for clinical laboratory values and vital signs.

End of Study is defined as the last available assessment during the study, including double-blind and safety follow-up period. End of Study results will be presented in analysis tables for safety parameters, including but not limited to electrocardiograms, clinical laboratory values, and vital signs.

ET = early termination.

The following general conventions for repeated or unscheduled assessments will apply unless otherwise specified:

- The latest non-missing assessment within any analysis window will be flagged as the analysis value for any summaries by analysis visit
- All postbaseline assessments will be considered for PCS categorization
- All assessments will be included in respective listings

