#### **Continuous Descriptives and Shift Table Parameters** 6.5.2.3

The following laboratory parameters will be summarized:

Table 6–9	Clinical Descriptive and Shift Table Parameters
-----------	-------------------------------------------------

Category	Parameters
Hematology	Hemoglobin; hematocrit; red blood cell count; red blood cell indices (mean corpuscular volume, mean corpuscular hemoglobin, mean corpuscular hemoglobin concentration); white blood cell count, including differential (neutrophils, lymphocytes, monocytes, eosinophils, and basophils); platelet count
Chemistry	Sodium, potassium, chloride, bicarbonate, glucose, blood urea nitrogen, creatinine, total bilirubin, alkaline phosphatase, aspartate aminotransferase, alanine aminotransferase, lactate dehydrogenase, creatine kinase, total protein, albumin, calcium, phosphorus, uric acid, total cholesterol. The estimated glomerular filtration rate will be calculated by the central laboratory.
Urinalysis	Urine dipstick for specific gravity, pH

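### The only PCS criterion for urine specific gravity in SAP Table 6–7 sets a limit of at least 1.10, which no dipstick reading can exceed if the scale ends below that

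*SAP*

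**What the plan says.** SAP 6.5.2.1 states the rule: "Laboratory assessments values meeting any of the following PCS low or PCS high criteria will be categorized as PCS". The limits are in Table 6–7. For urine specific gravity the low cell is empty and the high cell is a multiple of the ULN: "Specific gravity _ $> 1.1 \times ULN". The table footnote leaves the ULN to the laboratory ("normal value provided by laboratory"), and neither document gives a number for it.

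Both documents name the method. Protocol Table 6–1 (section 6.4.3) lists "Urine dipstick for specific gravity, pH, protein, glucose, ketones, bilirubin, and blood", and SAP Table 6–9 (section 6.5.2.3) lists "Urine dipstick for specific gravity, pH" among the parameters for continuous descriptives and shift tables. SAP 6.2.2 adds that "All postbaseline assessments will be considered for PCS categorization", and that every assessment goes into the listings.

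Table 6–7 also has a row for triglycerides: "Triglycerides mmol/L $> 2.0 \times ULN". The chemistry panels in Protocol Table 6–1 and SAP Table 6–9 include total cholesterol but not triglycerides.

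**The concern.** A multiplier such as 1.1 × ULN suits a quantity measured from a true zero, and Table 6–7 uses it for several of these, including sodium, calcium and hemoglobin. Specific gravity does not start at zero. It is the density of urine relative to water, so its floor is about 1, and normal and abnormal values alike lie in a narrow band just above that floor. Raising the ULN by 10% moves the limit by more than 0.10 on a scale whose useful width is a few hundredths.

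If the limit lies beyond the range of the dipstick, the criterion cannot be met. A zero count in the PCS analysis would then follow from the rule and not from the patients. A reader who did not check the threshold could take it as a negative safety finding.

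**Working it through.** **Inputs from the documents.** PCS limit: more than 1.1 × ULN, no low limit (SAP Table 6–7). ULN: supplied by the laboratory, no value given. Method: dipstick (Protocol Table 6–1, SAP Table 6–9).

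**Assumptions, because the documents give no figures.** ULN between 1.020 and 1.040, with 1.000 (pure water) as the lowest conceivable value. Top dipstick reading between 1.030 and 1.060.

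The plan states only a multiplier, so there is no numerical limit of its own to reproduce.

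**Step 1: the limit.** Limit = 1.1 × ULN. Excess ratio = (limit − 1) / (ULN − 1), which is how many times the normal limit's excess over water a patient would need.

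| ULN | Limit | Excess ratio |
|---|---|---|
| 1.000 | 1.100 | not defined |
| 1.020 | 1.122 | 6.1 |
| 1.025 | 1.1275 | 5.1 |
| 1.030 | 1.133 | 4.43 |
| 1.035 | 1.1385 | 3.96 |
| 1.040 | 1.144 | 3.6 |

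At a ULN of 1.030, for example, the excess over water would have to be above 0.133 against 0.030 at the ULN, and 0.133 / 0.030 = 4.43.

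**Step 2: can a reading exceed it?** A top reading T exceeds the limit only if ULN < T / 1.1.

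| Top reading T | ULN would have to be below |
|---|---|
| 1.030 | 0.936 |
| 1.040 | 0.945 |
| 1.060 | 0.964 |

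Each of these ULNs is lighter than water. The conclusion therefore does not depend on where in the assumed ranges the true values lie. What it needs is a top reading below 1.10.

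**Step 3: is there another route to PCS?** SAP 6.5.2.1 classes a value as PCS only through a listed low or high criterion, and the low cell is empty. There is no other route.

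**Step 4: triglycerides.** Table 6–7 has 21 chemistry rows. Protocol Table 6–1 has 20 chemistry parameters (19 analytes plus estimated glomerular filtration rate). Matched one to one, the only difference is triglycerides. SAP Table 6–9 repeats the protocol panel.

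**The case against.** The strongest reply is that the documents give neither the dipstick scale nor the laboratory's ULN. A reader might infer that the row must read zero as a matter of fact. The documents support only that the limit is at least 1.10. That no reading gets there is an assumption about the dipstick, though a safe one on any plausible scale. This part of the reply stands, and the conclusion is worded accordingly.

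A reader might also infer that a drug effect on specific gravity would go unseen, or expect a printed row of 0% in all six arms, or put the result as 0 of about 810 patients. The documents do not support these:

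- Specific gravity is in the descriptive and shift summaries of Table 6–9, and all assessments are listed.
- The layout of the PCS display cannot be checked: Table 5–20 is named in the SAP's list of tables but its content is not in the available text, and table specifications are held in a separate document.
- About 810 is the number to be randomized. Safety analyses use the Safety Population, and PCS classification uses postbaseline assessments.

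For triglycerides, it is tempting to say that the row can hold no data and should be deleted. Protocol 6.4.3 allows unscheduled laboratory tests for patient safety, so an off-panel value could reach the row. The documents show a mismatch and do not show which side is in error. An empty row would mislead no one.

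The threshold defect survives all of this. None of these points gives the specific gravity criterion a way to be met.

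**Conclusion.** The concern holds in a limited form. The specific gravity criterion is at least 1.10 for any possible ULN, and 1.122 to 1.144 for an assumed ULN of 1.020 to 1.040. Provided that the dipstick's top reading is below 1.10, no value in any arm can be classed as PCS, and a zero count is uninformative about safety. Among the planned laboratory outputs, a change in specific gravity could then be seen only in the Table 6–9 summaries and the listings.

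Severity is low. This is one row of a descriptive safety table. Efficacy, alpha, sample size and hepatic monitoring are untouched. The triglycerides mismatch is established by the documents alone but is housekeeping, and the conclusion does not rest on it.

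**What to change.** Before database lock, do one of two things with the specific gravity row of SAP Table 6–7: replace the criterion with one that lies within the central laboratory's reporting range for the dipstick, or remove the row and rely on the descriptive and shift tables. The first option requires the reporting range and ULN from the central laboratory, and the SAP should state the resulting limit as a number.

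At the same time, reconcile the triglycerides row with Protocol Table 6–1 and SAP Table 6–9, so that the three lists agree or the difference is explained.

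The cost is an edit to two rows of one SAP table. No new data are needed. SAP 5.1 places approval of the SAP before database lock, so the change fits the planned sequence.
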